8.6 Safety Follow-Up Visit

Assessments at this visit include:

- Vital signs; pulse rate, systolic and diastolic blood pressures, and temperature (respiration rate will be assessed in addition if the subject experiences an AE)
- Blood samples will be collected for hematology, biochemistry analyses, and pregnancy test
- Urine will be collected for urinalysis
- Physical examination
- Plasma for CZP concentration and ADA_b
- Plasma for biomarkers
- Concomitant medication
- AEs
- Contact IXRS to indicate that subject has completed the SFU

8.7 Withdrawal Visit

Assessments to be conducted at the WD Visit are specified in [Section 8.3](#) for Week 96/WD.

8.8 Unscheduled Visit

It is at the Investigator's discretion to initiate an Unscheduled Visit, if deemed necessary by the Investigator for the subject's safety and well-being. At this visit, any of the following assessments may be performed dependent on the presenting reason:

- Vital signs
- Blood samples for hematology, biochemistry analyses, other testing such as for TB or CRP
- Urine for urinalysis and/or pregnancy testing (for women of childbearing potential)
- Physical examination
- Concomitant medication
- AEs
- TB questionnaire

9 ASSESSMENT OF EFFICACY

Most of these tools have been used in AS studies but data support their use also in axSpA studies (Haibel et al, 2008; Barkham et al, 2009).

9.1 Assessment of primary and secondary efficacy variables

9.1.1 ASAS20, ASAS40, ASAS 5/6 response, and ASAS partial remission

The ASAS20 is defined as an improvement of at least 20% and absolute improvement of at least 1 unit on a 0 to 10 NRS in at least 3 of the 4 following domains:

- Patient's Global Assessment of Disease Activity (see [Section 9.2.3](#))

- Pain assessment (the total spinal pain NRS score)
- Function (represented by BASFI, [Section 9.1.3](#))
- Inflammation (the mean of the BASDAI questions 5 and 6, [see [Section 9.1.2](#)] concerning morning stiffness intensity and duration)

and absence of deterioration in the potential remaining domain (deterioration is defined as a relative worsening of at least 20% and an absolute worsening of at least 1 unit).

The ASAS criteria for 40% improvement are defined as relative improvements of at least 40%, and absolute improvement of at least 2 units on a 0 to 10 NRS in at least 3 of the 4 domains and no worsening at all in the remaining domain.

The ASAS 5/6 response is defined as at least 20% improvement in 5 of 6 domains, including spinal mobility (lateral spinal flexion) and CRP as more objective measures (Brandt et al, 2004).

The ASAS PR response is defined as a score of ≤ 2 units on a 0 to 10 unit scale in all 4 domains listed above for ASAS20.

The ASAS variables will be calculated at Weeks 0, 2, 4, 12, 24, 36, 48, 52, 60, 72, 84, and 96.

The ASAS assessments per visit are described in the schedule of study assessments [Table 5.1](#).

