8.3 Weeks 2 to 96/WD onsite visits

8.3.1 Weeks 2, 4, 12, 24, 32, 36, 48, 52, 60, 72, 84, and 96/WD (\pm 3 Days)

Assessments at these onsite visits include:

- Vital signs: pulse rate, systolic and diastolic blood pressures, temperature will be measured (all visits). If a subject experiences an AE, respiration rate will be measured in addition.
- Blood samples will be collected for hematology and biochemistry analyses (at Weeks 12, 24, 32, 36, 60, 72, 84, and at Week 96/WD), and CRP (at Weeks 2, 4, 12, 24, 32, 36, and from Week 52 onwards every 4 weeks only).
- Urine pregnancy testing for women of childbearing potential will be at Week 96/WD only.

- Urine will be collected for urinalysis (at Weeks 12, 24, 32, 36, 48, 60, 72, 84, and at Week 96/WD).
- Physical examination (at Weeks 12, 24, 36, 48, 60, 72, 84, and at Week 96/WD), including weight at Week 48 and at Week 96/WD.
- Extra-articular assessments (at Weeks 4, 12, 24, 36, 48, 52, 60, 72, 84, and at Week 96/WD).
- TB test (at Week 48 and at Week 96/WD only).
- TB questionnaire (at Weeks 12, 24, 36, 48, 60, 72, 84, and at Week 96/WD).
- MRI (at Week 48 and at Week 96/WD only).
- BASMI and spinal mobility (at Weeks 2, 4, 12, 24, 36, 48, 52, 60, 72, 84, and at Week 96/WD only).
- BASDAI (at Weeks 2, 4, 12, 24, 32, 36, 52, 60, 72, 84, and at Week 96/WD).
- BASFI (at Weeks 2, 4, 12, 24, 36, 60, 72, 84, and at Week 96/WD only).
- SF-36 (at Weeks 4, 12, 24, 36, 60, 72, 84, and at Week 96/WD only).
- ASQoL (at Weeks 2, 4, 12, 24, 36, 60, 72, 84, and at Week 96/WD only).
- EQ-5D (at Weeks 12, 24, 36, 60, 72, 84, and at Week 96/WD only).
- IBD-Q (at Week 96/WD only).
- MASES (at Weeks 12, 24, 36, 48, 60, 72, 84, and at Week 96/WD only).
- Total spinal pain NRS and nocturnal spinal pain NRS (at Weeks 2, 4, 12, 24, 36, 52, 60, 72, 84, and at Week 96/WD only).
- Swollen and tender joint counts (at Weeks 2, 4, 12, 24, 36, 48, 52, 60, 72, 84, and at Completion at Week 96/WD only).
- PtGADA (at Weeks 2, 4, 12, 24, 32, 36, and from Week 52 onwards every 4 weeks only).
- PhGADA (at Weeks 12, 24, 36, 48, 52, 60, 72, 84, and at Week 96/WD only).
- WPS (at Weeks 4, 12, 24, 36, 48, 60, 72, 84, and at Week 96/WD only).
- Resource utilization (at Weeks 12, 24, 36, 48, 60, 72, 84, and at Week 96/WD only).
- Plasma for CZP concentration and ADAb (at Weeks 4, 12, 24, 60, 72, 84, and at Week 96/WD only).
- Plasma for biomarkers (at Weeks 4, 12, 24, 60, 72, 84, and at Week 96/WD only), if applicable.

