- BASDAI at Escape Weeks 0, 2, 4, and every 4 weeks thereafter until the final assessment visit at Week 96/WD
- BASFI at Escape Weeks 0, 2, 4, 12, and every 12 weeks thereafter until the final assessment visit at Week 96/WD
- SF-36 at Escape Weeks 0, 4, 12, and every 12 weeks thereafter until the final assessment visit at Week 96/WD
- ASQoL at Escape Weeks 0, 2, 4, 12, and every 12 weeks thereafter until the final assessment visit at Week 96/WD
- EQ-5D at Escape Weeks 0, 4, 12, and every 12 weeks thereafter until the final assessment visit at Week 96/WD
- MASES at Escape Weeks 0, 2, 4, 12, and every 12 weeks thereafter until the final assessment visit at Week 96/WD.
- Total spinal pain NRS and nocturnal spinal pain NRS at Escape Weeks 0, 2, 4, 12, and every 12 weeks thereafter until the final assessment visit at Week 96/WD
- PtGADA at Escape Weeks 0, 2, 4, and every 4 weeks thereafter until the final assessment visit at Week 96/WD
- PhGADA at Escape Weeks 0, 2, 4, 12, and every 12 weeks thereafter until the final assessment visit at Week 96/WD
- WPS at Escape Weeks 0, 4, 12, and every 12 weeks thereafter until the final assessment visit at Week 96/WD
- Resource utilization at Escape Weeks 0, 4, 12, and every 12 weeks thereafter until the final assessment visit at Week 96/WD
- Plasma for CZP concentration and ADAbs at Escape Weeks 0, 2, 4, 12, and every 12 weeks thereafter until the final assessment visit at Week 96/WD
- Plasma for biomarkers at Escape Weeks 0, 2, 4, 12, and every 12 weeks thereafter until the final assessment visit at Week 96/WD, if applicable.
- Concomitant medication at Escape Weeks 0, 2, 4, 12, and every 12 weeks thereafter until the final assessment visit at Week 96/WD
- AEs
- Contact IXRS to obtain next kit numbers
- Study drug administration (after all other visit assessments are completed and laboratory samples are drawn) at site and study drug self-injection at home

Refer to [Table 5.1](#) and [Section 8.3](#) for the final assessments due at Week 96/WD.

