9.2.10 Resource utilization

Study specific questionnaires (standard eCRF modules) will be used to capture data regarding resources utilization during the study, ie:

- Concomitant Medical Procedures
- Health care provider consultations not foreseen by the protocol
- Hospitalizations/Emergency Room visit (including length of stay)

Site personnel should obtain information from the subject and corroborate data with known AEs and SAEs in order to complete this survey as described in the schedule of study assessments [Table 5.1](#). The recall period for the questionnaire will be the previous 4 weeks.

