14.2 General statistical considerations

All efficacy analyses for Part B will be performed using the RS. The FAS and PPS will be used for a sensitivity analysis on the primary endpoint only. Efficacy summaries for variables collected in Part A will be based on the OLS.

Summaries at the Week 48 timepoint for laboratory data and data collected via electronic device (Site Tablet) will be based on the assessments conducted 3 to 5 days prior to the Week 48 clinic visit.

The statistical analysis of the primary efficacy variable will account for the testing of multiple doses by using a fixed sequence testing procedure. The proportion of subjects who do not experience a flare (where flare is defined as ASDAS ≥ 2.1 on 2 consecutive visits or ASDAS > 3.5 at any visit) will be compared between each CZP dose and placebo. The predefined order of

hypotheses testing, each at a 2-sided 0.05 significance level for the comparison between the given CZP dose and placebo, will be performed in the sequence shown below:

1. CZP 200mg Q2W vs placebo
2. CZP 200mg Q4W vs placebo

The second test will be performed irrespective of whether the first test is significant at the 0.05 level or not. However, the second test will be interpreted as statistically significant only if the first test is significant at the 0.05 level as well.

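### ASAS response is listed for Week 52, where BASFI is not collected, so ASAS20, ASAS40 and partial remission cannot be confirmed there; a minor second point is a 4-week resource-use recall at 12-weekly visits

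*Protocol*

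**What the plan says.** **ASAS at Week 52.** Section 9.1.1 fixes the calculation timepoints: "The ASAS variables will be calculated at Weeks 0, 2, 4, 12, 24, 36, 48, 52, 60, 72, 84, and 96". The same section makes BASFI one of the four domains ("Function (represented by BASFI") and requires a score of 2 or less "in all 4 domains listed above for ASAS20" for partial remission. ASAS20 and ASAS40 need improvement in at least three domains and also a check that the remaining one has not worsened. Section 8.3.1 schedules "BASFI (at Weeks 2, 4, 12, 24, 36, 60, 72, 84, and at Week 96/WD only"). Baseline is added by Section 8.2 and the visit shortly before Week 48 by Section 8.3.2. Week 48 summaries of tablet data "will be based on the assessments conducted 3 to 5 days prior to the Week 48 clinic" visit, so BASFI does exist for Week 48. The home-nurse list in Section 8.4.2 contains no BASFI.

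Section 14.3.3.2 analyses ASAS response by logistic regression at timepoints outside the secondary analyses, with a model like that of Section 14.3.2.2, where missing status counts as nonresponse. Section 14.6 repeats that rule for binary variables in general.

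**Resource use.** Section 9.2.10 says the modules are there to capture utilization over the course of the study, and then: "The recall period for the questionnaire will be the previous 4 weeks". Section 8.3.1 has "Resource utilization (at Weeks 12, 24, 36, 48, 60, 72, 84, and at Week 96/WD only"). After a flare, Section 8.5 has "Resource utilization at Escape Weeks 0, 4, 12, and every 12 weeks thereafter", up to the final visit.

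**The concern.** Week 52 is the first ASAS timepoint listed after randomization at Week 48. Everyone in Part B enters in sustained remission. A by-visit table showing no ASAS20, ASAS40 or partial remission responders four weeks later, in all three arms, would be an artefact of the visit schedule. An analysis plan can decide how to present this, but it cannot supply a questionnaire that was never given.

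For resource use, the stated aim is wider than the recall window can serve. Events in 8 of every 12 weeks are never asked about. The questionnaire is also given more often after a flare, so the amount of time covered depends on the outcome that the treatments are expected to change. Resource utilization is a listed objective (Section 3.3), and lower healthcare cost is part of the rationale (Section 2.5).

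**Working it through.** **1. ASAS components at the listed visits.** The check uses the visit lists in Sections 8.2, 8.3.1 and 8.3.2, counting the visit 3 to 5 days earlier as Week 48. It does not rely on the columns of Table 5.1, which do not survive text extraction cleanly.

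| Component | Collected at Week 52? |
|---|---|
| PtGADA | yes |
| Total spinal pain | yes |
| BASDAI (questions 5 and 6) | yes |
| BASFI | **no** |
| BASMI/spinal mobility and CRP (for ASAS 5/6) | yes |

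The plan's figure is 12 timepoints. All four domains are present at 11 of them (Weeks 0, 2, 4, 12, 24, 36, 48, 60, 72, 84, 96). Week 52 is the only failure.

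Consequences at Week 52, by criterion:

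- *Partial remission* needs all four domains, so it cannot be confirmed for anyone. A score above 2 in any observed domain does settle nonresponse.
- *ASAS20 and ASAS40*: even if all three observed domains improve enough, BASFI is the remaining domain and must be checked for worsening, so response is not confirmed. Two or more observed domains below threshold settle nonresponse. There is one ceiling exception: a Baseline BASFI above 10/1.2 = 8.33 leaves no room for a 20% worsening (ASAS20), and a Baseline of 10 leaves none at all (ASAS40). A derivation that simply requires BASFI would not use this.
- *ASAS 5/6* needs five of six domains, so it can be met if all five observed domains improve.

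With missing status set to nonresponse, ASAS20, ASAS40 and partial remission are 0% in each arm. With no responders in any arm, the treatment odds ratios cannot be estimated. Observed-case summaries do not help: those who can be classified are nonresponders, or nobody is classified.

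**2. Resource-use coverage.** Coverage is the union of the 4-week windows before each scheduled assessment, divided by elapsed weeks.

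- No flare, whole study: 8 visits × 4 = 32 of 96 weeks, 33%.
- No flare, Part B (Weeks 60, 72, 84, 96): 4 × 4 = 16 of 48, 33%.
- Escaper, using the protocol's own example of Escape Week 0 at Week 62 (assessments at 60, 62, 66, 74, 86, 96): 6 + 4 + 4 + 4 + 4 = 22 of 48, 46%. The 6 is the overlapping pair at Weeks 60 and 62.
- Escape Week 0 at each even week from 52 to 84: 20 to 24 of 48, that is 42% to 50%.

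**3. Effect on a pooled total by arm.** Section 14.8 assumes 45%, 75% and 80% without a flare on placebo, Q4W and Q2W. Assume equal and constant true use, and that every flaring subject follows the escape schedule. Mean coverage in an arm is p × 16/48 + (1 − p) × c, where p is the non-flare proportion and c is escaper coverage.

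| c | Placebo | Q4W | Q2W | Placebo/Q4W | Placebo/Q2W |
|---|---|---|---|---|---|
| 20/48 | 37.9% | 35.4% | 35.0% | 1.07 | 1.08 |
| 22/48 | 40.2% | 36.5% | 35.8% | 1.10 | 1.12 |
| 24/48 | 42.5% | 37.5% | 36.7% | 1.13 | 1.16 |

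**The case against.** On ASAS, the best answer is that Week 52 response is only an other efficacy variable. Section 4.1.3.2 limits these variables to visits where the assessment is performed, and Section 9.1.1 itself points to Table 5.1. A questionnaire scheduled for nobody is not ordinary missing data, so the imputation rule in Section 14.6, which is worded as a general rule with room for exceptions, need not apply. That is a sensible way to run the analysis, but it is not what the text settles: Section 9.1.1 names Week 52 explicitly, and a general phrase elsewhere does not cancel it.

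A reader might infer that ASAS status at Week 52 is undetermined for every subject, or that every ASAS criterion fails. Neither is supported: many nonresponders can be identified from the observed domains, and ASAS 5/6 remains attainable.

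On resource use, the defence is stronger. Sections 14.3.3.2 and 14.3.3.3 lead to descriptive summaries by visit, with flared subjects summarized separately. No cumulative Part B total or between-arm test is stated. At any single assessment the window is four weeks for everyone. Sites are told to corroborate against adverse events, and inpatient admissions for an adverse event are reported as SAEs (Section 12.2.1) whatever the recall window. A short recall is also a legitimate choice in favour of accuracy.

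Two stronger readings therefore fail. One is that resource use would be undercounted by two thirds: that holds at most for items with no other source, such as unplanned consultations or emergency visits without admission. The other is that the arm comparison is biased by 1.25 to 1.5 times (20/16 to 24/16): that ratio compares one escaper with one non-escaper, and escapers occur in all three arms.

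**Conclusion.** The Week 52 conflict is real and sits in the current text: one of 12 stated ASAS timepoints cannot be delivered for ASAS20, ASAS40 or partial remission, solely for want of BASFI. The 0% rates and non-estimable model follow if nonresponse imputation is applied there as written. The reach is limited. The primary endpoint rests on ASDAS, which does not use BASFI, and the secondary ASAS endpoints are at Week 96 and Escape Week 12, where BASFI is collected.

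The resource-use point is minor. The schedule yields 4-week snapshots, not use over the study. Harm arises only if the snapshots are summed over Part B. The total would then be incomplete and about 1.1 times higher on placebo than on either CZP arm with no true difference (range 1.07 to 1.16). This assumes the Section 14.8 flare rates, equal and constant true use, and no capture other than recall.

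**What to change.** 1. **ASAS.** Either delete Week 52 from the list in Section 9.1.1 and from the by-visit ASAS analyses under Section 14.3.3.2, or add BASFI at Week 52 in Section 8.3.1 and Table 5.1. The first is a text change and leaves 11 of 11 timepoints deliverable. The second adds a 10-item questionnaire to an existing onsite visit where other tablet questionnaires are already completed, and makes 12 of 12 deliverable.
2. **Resource use.** Either set the recall in Section 9.2.10 to the interval since the last resource-utilization assessment, with event dates recorded, in both the regular and the escape schedules; or keep four weeks and state that the data are snapshots, not to be summed or compared between arms as totals. The first covers 96 of 96 weeks at the price of eCRF wording and a longer recall of up to 12 weeks, which may be less accurate. The second costs a sentence and narrows the stated aim.

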9.1.2 Bath ankylosing spondylitis disease activity index (BASDAI)

The most common instrument used to measure the disease activity of AS from the subject's perspective and in the broad AxSpA population is the BASDAI (van Tubergen et al, in press 2015; Garrett et al, 1994). The BASDAI is a validated self-reported instrument which consists of six 10-unit horizontal NRSs to measure severity of fatigue, spinal and peripheral joint pain and swelling, enthesitis, and morning stiffness (both severity and duration, respectively) over the last week. The final BASDAI score ranges from 0 to 10, with lower scores indicating lower disease activity. The minimal clinically important difference (MCID) used to interpret scores is 10mm on a VAS or 22.5% of the Baseline score (Pavy et al, 2005). An MCID of 1 unit will be selected for the NRS version.

The BASDAI 50 is defined as an improvement of at least 50% in the BASDAI response.

The BASDAI is calculated as follows:

$$\frac{Q1 + Q2 + Q3 + Q4 + \frac{(Q5+Q6)}{2}}{5}$$

Fatigue item of the BASDAI

Fatigue as a major symptom of AS can effectively be measured with single item questions such as the BASDAI item (van Tubergen et al, 2002b). This item has shown moderate to good reliability and responsiveness (van Tubergen et al, 2002b). The same MCID will be used for the fatigue item of the BASDAI as for the total BASDAI score, ie, a change of 1 unit on the NRS.

The BASDAI assessments per visit are described in the schedule of study assessments [Table 5.1](#).

9.1.3 Bath ankylosing spondylitis functional index (BASFI)

The BASFI is a validated disease-specific instrument for assessing physical function (van Tubergen et al, in press 2015; Calin et al, 1994, van der Heijde et al, 2005). The BASFI comprises 10 items relating to the past week. The NRS version will be used for the answering options of each item on a scale of 0 (“Easy”) to 10 (“Impossible”) (van Tubergen et al, 2002a). The BASFI is the mean of the 10 scores such that the total score ranges from 0 to 10, with lower scores indicating better physical function. The MCID used to interpret scores is 7mm on a 0 to 100mm VAS or 17.5% of the Baseline score (Pavy et al, 2005); an MCID of 1 unit will be used for the NRS version.

The BASFI assessments per visit are described in the schedule of study assessments [Table 5.1](#).

9.1.4 MRI assessments

Magnetic resonance imaging of the spine and sacroiliac joints will be performed at Screening, Week 48, Week 96, or WD Visit if MRI was performed more than 12 weeks prior to WD.

Magnetic resonance imaging will be assessed centrally and scoring will be done by 2 independent readers, who are blinded to both the order of the scans and to the treatment group, using a previously reported scoring system. In addition, a single reader assessment will be performed for change from Baseline (Week 48) evaluation in sacroiliac SPARCC and ASpIMRI-a in the Berlin-modification scores for all subjects that entered Part A.

According to the ASAS/OMERACT definition, the presence of bone marrow oedema (BMO) or osteitis is highly suggestive of SpA that is located in the typical anatomical areas (subchondral or periarticular bone marrow). There must be either more than 1 BMO lesion on 1 slice or a lesion that is present on at least 2 consecutive slices (Rudwaleit et al, 2009b). The ASAS/OMERACT definition will be used for the classification of all Screening MRIs by the central readers. In practice, this is very similar to the SPARCC SIJ ≥ 2 definition of MRI which requires at least 2 BMO lesions to be present. A recent paper showed that the sensitivity and specificity of the ASAS/OMERACT and SPARCC SIJ score ≥ 2 definitions of MRI positive were identical (sensitivity 0.80, specificity 0.76) (Weber et al, 2014). For the evaluation of the inflammatory changes over time, the SPARCC SIJ definition will be applied for all MRI images.

The SPARCC scoring method for lesions found on the MRI is based on an abnormal increased signal on the short-tau-inversion recovery (STIR) sequence, representing BMO (defined as an increased signal in bone marrow on a T2-weighted sequence, reflecting an increased concentration of “free water” related to a bone lesion). Total SIJ SPARCC scores can range from 0 to 72.

In addition to the method mentioned above, MRIs may be evaluated using other reading criteria.

9.1.5 Bath ankylosing spondylitis metrology index

The BASMI characterizes the spinal mobility of subjects with AS. The BASMI is a disease-specific measure consisting of 5 clinical measures to reflect subject axial status: cervical rotation; tragus to wall distance; lateral spinal flexion; modified Schober test; intermalleolar distance. Each of the 5 movements is scored according to the linear BASMI definition. The mean of the 5 scores provides the BASMI score. The higher the BASMI score the more severe the subject’s limitation of movement due to their axSpA.

The BASMI assessments per visit are described in the schedule of study assessments [Table 5.1](#).

9.1.6 Total and nocturnal spinal pain NRS

The pain in the spine due to AS (ie, “How much pain of your spine due to spondylitis do you have?”); and pain in the spine at night due to AS (ie, “How much pain of your spine due to spondylitis do you have at night?”) (Sieper et al, 2009; van der Heijde et al, 2005; CPMP/EWP/556/95). Usually, a 10% difference (ie, a 1-point difference on a NRS ranging from 0 to 10) is considered the MCID used to interpret scores (Dworkin et al, 2008). Pain experienced by axSpA subjects has also been measured with this assessment (Haibel et al, 2008).

The pain NRS assessments per visit are described in the schedule of study assessments [Table 5.1](#).

